## Appendix 5      Group 2: Example Time Schedule for Procedures During the Baseline Visit

Note: This is a sample schedule and time of arrival at the study center can be shifted as needed. Individual assessments should be performed at approximately the same time of day across study visits.

Baseline Visit	
Approximate Time	Procedure/Activity
8:00	
Subject arrives at study center
 
Assess any updates to medical history and changes in concomitant medications. Record all AEs that occur after the ICF was signed. Verify and ensure PD and sleep medications were taken and continue to be taken appropriately. For subjects currently receiving treatment for OSA, review OSA therapy device usage to ensure adequate compliance.
 
Administer the ESS Questionnaire
 
Administer the C-SSRS Questionnaire
 
Body temperature, respiratory rate, and at least 2 sets of blood pressure and pulse in seated position; then blood pressure and pulse at 1 and 3 minutes after standing
 
Physical examination and weight
 
Safety laboratory blood samplesa
 
Urine sample for urinalysisa
 
Urine pregnancy test (for all females of childbearing potential)
 
Alcohol breath screening test

9:15	Light breakfast
10:00	At least 2 sets of blood pressure and pulse in seated position; then blood pressure and pulse at 1 and 3 minutes after standing
10:30	Complete the FSS, Apathy Scale, and SCOPA-cog Questionnaires
11:00	
At least 2 sets of blood pressure and pulse in seated position; then blood pressure and pulse at 1 and 3 minutes after standing
 
ECG
 
Complete the CGIs
 
Administer the MDS-UPDRS (Parts III and IV)b

AE = adverse event; CGIs = Clinical Global Impression of Severity; C-SSRS = Columbia-Suicide Severity Rating Scale; ECG = electrocardiogram; ESS = Epworth Sleepiness Scale; ICF = informed consent form; I/E = inclusion/exclusion; MDS-UPDRS = Movement Disorders Society-Unified Parkinson's Disease Rating Scale; FSS = Fatigue Severity Scale; PD = Parkinson's disease; SCOPA cog = Scales for Outcomes in Parkinson's disease-cognition

a If the Baseline visit occurs outside of the screening window (i.e., >29 days after the Screening visit), obtain blood samples for serum chemistry and hematology and a urine sample for urinalysis.

b When feasible, the MDS-UPDRS (Parts III and IV) is to be performed at approximately the same time for each subsequent visit while the subject is in the "on" state.

## Appendix 6      Group 2: Example Time Schedule for Procedures at Visits 3, 4, 5, or 6

Note: This is a sample schedule and time of arrival at the study center can be shifted as needed. Individual assessments should be performed at approximately the same time of day across study visits.

Visits 3, 4, 5, and 6		
Time Relative to Dosing	Approximate Time	Procedure/Activity
~ -1 h	8:00	Subject arrives at study center Record all concomitant medications taken since last visit. Record all AEs. Verify and ensure PD medications, sleep medications allowed by the protocol, and study drug (as specified in Section 5.3 of the protocol) were taken and continue to be taken appropriately. For subjects currently receiving treatment for OSA, review OSA therapy device usage to ensure adequate compliance. Body temperature, respiratory rate, and at least 2 sets of blood pressure and pulse in seated position; then blood pressure and pulse at 1 and 3 minutes after standing ECG Physical examination and weight Safety laboratory blood samples Urine sample for urinalysis Urine pregnancy test (for all females of childbearing potential) Alcohol breath screening test
0 h	9:00	Dosing
~ 0.25 h	9:15	Light breakfast
~ 1 h	10:00	At least 2 sets of blood pressure and pulse in seated position; then blood pressure and pulse at 1 and 3 minutes after standing
~ 1.5 h	10:30	Complete the ESS, PGIC, FSS, Apathy Scale, SCOPA-cog, and C-SSRS Questionnaires
~ 2 h	11:00	At least 2 sets of blood pressure and pulse in seated position; then blood pressure and pulse at 1 and 3 minutes after standing ECG Complete the CGIC Administer the MDS-UPDRS (Parts III and IV) a

AE = adverse event; CGIC = Clinical Global Impression of Change; C-SSRS = Columbia-Suicide Severity Rating Scale; ECG = electrocardiogram; ESS = Epworth Sleepiness Scale; MDS-UPDRS = Movement Disorders Society-Unified Parkinson's Disease Rating Scale; FSS = Fatigue Severity Scale; PD = Parkinson's disease; PGIC = Patient Global Impression of Change; SCOPA cog = Scales for Outcomes in Parkinson's disease-cognition

a When feasible, the MDS-UPDRS (Parts III and IV) is to be performed at approximately the same time for each subsequent visit while the subject is in the "on" state.

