### 1.3.1 Clinical Pharmacokinetics and Product Metabolism

JZP-110 is eliminated primarily via the renal route, with at least 90% of the dose being excreted as unchanged drug within 48 hours. Following single dosing and repeated doses administered twice daily, JZP-110 exposure was dose-proportional, absorption (time to maximum plasma concentration [ $t_{max}$ ]: 1.3 to 3.0 hours) and elimination ( $t_{1/2}$ : 5 to 7.6 hours) were relatively rapid, and steady state was reached in 3 days. JZP-110 displayed linear PK during 14 days of dosing over the dose range of 200 to 1000 mg per day. Limited accumulation and no enzyme auto-induction were evident.

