**Subjects enrolling in the study after Amendment 2 implementation will not undergo PK evaluation.**

On admission to the investigative site in the morning (at approximately 8:00 AM) on Days 7 ( $\pm 1$ ), 14 ( $\pm 1$ ), 21 ( $\pm 1$ ), and 28 ( $\pm 1$ ), complete the following (as listed in Appendix 3):

- Record all concomitant medications, including OTC medications, health, and dietary supplements taken since the last visit. Record all AEs. Verify PD medications, sleep medications allowed by the protocol, and study drug (as specified in [Section 5.3](#) of the protocol) were taken and continue to be taken appropriately. For subjects currently receiving treatment for OSA, review OSA therapy device usage to ensure adequate compliance.
- Administer the ESS Questionnaire.
- Administer the MDS-UPDRS (Parts III and IV). When feasible, the MDS-UPDRS (Parts III and IV) is to be performed on the same study day and approximate same time for each subsequent visit while the subject is in the “on” state.
- Complete the CGIc.
- Perform physical examination.
  - Obtain weight in ordinary indoor clothes (without shoes).
- Approximately 1 hour before dosing, obtain vital signs (systolic and diastolic blood pressure [seated and standing], pulse rate [seated and standing], respiratory rate, and body

temperature), including at least 2 sets of blood pressure and pulse rate measurements in the seated position after the subject has been resting and seated for at least 5 minutes.

Next, standing blood pressure and pulse rate should be taken at 1 and 3 minutes after the subject has been standing.

- 12-lead ECG after the subject has been resting supine for at least 5 minutes.
- Obtain safety laboratory blood samples for serum chemistry and hematology tests and a urine sample for urinalysis.
- Obtain a urine sample for a pregnancy test for all females of childbearing potential (see [Table 1](#) for definitions of childbearing potential).
- Complete breath alcohol screen test.
- Observe study drug administration by the subject.
- Approximately 15 minutes after dosing, subjects may be served a light breakfast. Breakfast should be completed within 15 to 20 minutes.

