### **7.3 Group 2: Baseline and Treatment Phase Study Activities (Subjects Opting Out of the MWT Component of the Study)**

#### **7.3.1 Group 2: Baseline/Randomization/Visit 2 (Day -1)**

After a subject has successfully completed the screening procedures, he or she will return to the investigative site to complete his or her baseline procedures.

On admission to the study center in the morning (at approximately 8:00 AM on Day -1), complete the following (as listed in [Appendix 5](#)):

- Document the date(s) that excluded medications were discontinued and any other changes to concomitant medications since screening. Record all AEs that occur after the ICF was signed. Verify and ensure PD and sleep medications were taken and continue to be taken at the same dose and regimen. For subjects currently receiving treatment for OSA, review OSA therapy device usage to ensure adequate compliance.
- Administer the ESS Questionnaire.
- Administer the C-SSRS Since Last Visit Version and record the results.
- Obtain vital signs (systolic and diastolic blood pressure [seated and standing], pulse rate [seated and standing], respiratory rate, and body temperature), including at least 2 sets of blood pressure and pulse rate measurements in the seated position after the subject has been resting and seated for at least 5 minutes. Next, standing blood pressure and pulse rate should be taken at 1 and 3 minutes after the subject has been standing.
- Perform physical examination.
  - Obtain weight in ordinary indoor clothes (without shoes).
- If the Baseline visit occurs outside of the screening window (i.e., >29 days after the Screening Visit), obtain safety laboratory blood samples for serum chemistry and hematology tests and a urine sample for urinalysis. Record if the samples were collected with the subject fasted or nonfasted.
- Obtain a urine sample for a pregnancy test for all females of childbearing potential (see [Table 1](#) for definitions of childbearing potential).
- Complete breath alcohol screen test.
- A light breakfast may be served. Breakfast should be completed within 15 to 20 minutes.

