**Subjects enrolling in the study after Amendment 2 implementation will not undergo PK evaluation.**

On admission to the investigative site in the morning (at approximately 8:00 AM) on Days 7 ( $\pm 1$ ), 14 ( $\pm 1$ ), 21 ( $\pm 1$ ), and 28 ( $\pm 1$ ), complete the following (as listed in [Appendix 6](#)):

- Record all concomitant medications, including OTC medications, health, and dietary supplements taken since the last visit. Record all AEs. Verify PD medications, sleep medications allowed by the protocol, and study drug (as specified in [Section 5.3](#) of the

protocol) were taken and continue to be taken appropriately. For subjects currently receiving treatment for OSA, review OSA therapy device usage to ensure adequate compliance.

- Approximately 1 hour before dosing, obtain vital signs (systolic and diastolic blood pressure [seated and standing], pulse rate [seated and standing], respiratory rate, and body temperature), including at least 2 sets of blood pressure and pulse rate measurements in the seated position after the subject has been resting and seated for at least 5 minutes. Next, standing blood pressure and pulse rate should be taken at 1 and 3 minutes after the subject has been standing.
- 12-lead ECG after the subject has been resting supine for at least 5 minutes.
- Perform physical examination.
  - Obtain weight in ordinary indoor clothes (without shoes).
- Obtain safety laboratory blood samples for serum chemistry and hematology tests and a urine sample for urinalysis.
- Obtain a urine sample for a pregnancy test for all females of childbearing potential (see [Table 1](#) for definitions of childbearing potential).
- Complete breath alcohol screen test.
- Observe study drug administration by the subject.
- Approximately 15 minutes after dosing, subjects may be served a light breakfast. Breakfast should be completed within 15 to 20 minutes.
- Approximately 1 hour after dosing, obtain vital signs (systolic and diastolic blood pressure [seated and standing] and pulse rate [seated and standing]), including at least 2 sets of blood pressure and pulse rate measurements in the seated position after the subject has been resting and seated for at least 5 minutes. Next, standing blood pressure and pulse rate should be taken at 1 and 3 minutes after the subject has been standing.
- Administer the ESS Questionnaire.
- Complete the PGIC, FSS, Apathy Scale, and the SCOPA-cog.

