~ -1 h	8:00	Subject arrives at study center a Record all concomitant medications taken since last visit. Record all AEs. Verify and ensure PD medications, sleep medications allowed by the protocol, and study drug (as specified in Section 5.3 of the protocol) were taken and continue to be taken appropriately. For subjects currently receiving treatment for OSA, review OSA therapy device usage to ensure adequate compliance. a Administer the ESS Questionnaire a Administer the MDS-UPDRS (Parts III and IV) a,b Complete the CGIC a Physical examination and weight a Body temperature, respiratory rate, and at least 2 sets of blood pressure and pulse in seated position; then blood pressure and pulse at 1 and 3 minutes after standing ECG Safety laboratory blood samples a Urine sample for urinalysis a Urine pregnancy test (for all females of childbearing potential) a Alcohol breath screening test a
0 h	9:00	Dosing
~0.25 h	9:15	Light breakfast
~1 h	9:50	At least 2 sets of blood pressure and pulse in seated position; then blood pressure and pulse at 1 and 3 minutes after standing
~1 h	10:00c	Ask the subject the following question: "How long did you sleep last night?" Start first MWT trialc
~2 h	11:00	At least 2 sets of blood pressure and pulse in seated position; then blood pressure and pulse at 1 and 3 minutes after standing
~2.25 h	11:15	Complete the PGIC, FSS, Apathy Scale, SCOPA-cog, and C-SSRS Questionnaires a
~3 h	12:00	Start second MWT trial Light lunch served immediately after the end of the second trial
~4 h	13:00	At least 2 sets of blood pressure and pulse in seated position; then blood pressure and pulse at 1 and 3 minutes after standing
~5 h	14:00	Start third MWT trial
~6 h	15:00	At least 2 sets of blood pressure and pulse rate measurements in seated position; then standing blood pressure and pulse rate measurements at 1 and 3 minutes after standing ECG
~7 h	16:00	Start fourth MWT trial (optional)

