CGIC = Clinical Global Impression of Change; ECG = electrocardiogram; ESS = Epworth Sleepiness Scale; MDS-UPDRS = Movement Disorders Society-Unified Parkinson's Disease Rating Scale; MWT = maintenance of wakefulness test; FSS = Fatigue Severity Scale; PGIC = Patient Global Impression of Change; SCOPA cog = Scales for Outcomes in Parkinson's disease-cognition

JZP-110

Clinical Trial Protocol: JZP166-201 Amendment 2

Jazz Pharmaceuticals

---

- a These assessments can be performed the day before the MWT, provided it falls within the visit window. Individual assessments should be performed on the same study day at approximately the same time of day across study visits.
- b When feasible, the MDS-UPDRS (Parts III and IV) is to be performed on the same study day and approximate same time for each subsequent visit while the subject is in the “on” state.
- c The first MWT trial should be started approximately 1.5 to 3 hours after the time of the subject arising that morning.

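### In Group 2 the ESS moves from arrival at Baseline to about 1.5 h after dosing at Visits 3–6, against the protocol's own timing rule; moving it before the dose is a free improvement

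*Protocol*

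**What the plan says.** **Group 2, Baseline.** Protocol Section 7.3.1 opens its list with "On admission to the study center in the morning (at approximately 8:00 AM on Day -1), complete the following", and the ESS is among the first items. Appendix 5 places it in the 8:00 block, before breakfast.

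**Group 2, Visits 3–6.** Appendix 6 sets dosing at 9:00, breakfast at 9:15, and at 10:30 (about 1.5 h) the entry "Complete the ESS, PGIC, FSS, Apathy Scale, SCOPA-cog, and C-SSRS Questionnaires". Section 7.3.2 agrees: "Observe study drug administration by the subject", then breakfast, then "Approximately 1 hour after dosing, obtain vital signs", and only then the ESS.

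**Group 1.** "Administer the ESS Questionnaire" stands in the 8:00 block at Baseline (Section 7.2.1, Appendix 2) and in the 8:00 pre-dose block at Visits 3–6 (Section 7.2.2, Appendix 3). A footnote to Appendix 3 that covers the ESS adds: "These assessments can be performed the day before the MWT, provided it falls within the visit window".

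**Timing rule.** The notes to Appendices 5 and 6, and Section 7.3.2, state: "Individual assessments should be performed at approximately the same time of day across study visits".

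**Drug level.** Section 1.3.1 gives the time to maximum concentration as "1.3 to 3.0 hours) and elimination" half-life as 5 to 7.6 h.

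**Analysis.** The ESS model in SAP Section 16.1.4 has Baseline ESS, treatment, sequence and period, with a random subject effect. It has no term for Group or for time of assessment. Randomization is not stratified by Group (Protocol Section 5.4). Protocol Sections 9.12 and 9.15 allow results to be reported by Group, but SAP Sections 16.1.5 and 16.1.6 list no such ESS analysis.

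**The concern.** Group 2's on-treatment ESS is taken at a different clock time from its own Baseline, and at a different point relative to dosing from Group 1's scheduled slot. Because the body text and the sample schedule agree, this is not a slip in an example table. The protocol gives no reason for it.

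The second difference is the one that could matter. JZP-110 is a wake-promoting drug. If the way a subject feels while filling in the form colours the answers at all, a form completed near peak drug level would be coloured by the drug in active periods and not in placebo periods. That influence would be counted as part of the treatment effect on the key efficacy endpoint. It would act differently in the two Groups, which the model pools without distinction.

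**Working it through.** The plan states no figure on this point, so there is none to reproduce. The sample-size calculation is not involved. The check compares the schedules and then asks which parts of the timing difference survive in the drug–placebo contrast.

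**1. Schedules side by side** (clock times from Appendices 2, 3, 5 and 6; order confirmed in Sections 7.2.1, 7.2.2, 7.3.1 and 7.3.2)

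| | ESS at Baseline | ESS at Visits 3–6 | Relative to the 9:00 visit dose |
|---|---|---|---|
| Group 1 | 8:00 block (or the day before) | 8:00 block (or the day before the MWT) | about −1 h, or the previous day |
| Group 2 | 8:00 block | 10:30 | about +1.5 h |

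Clock-time shift in Group 2: 10:30 − 8:00 = 2.5 h. In Group 1, with arrival-block completion at both: 8:00 − 8:00 = 0 h.

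**2. Other Group 2 scales.** FSS, Apathy Scale and SCOPA-cog are at 10:30 at Baseline and at Visits 3–6. MDS-UPDRS is in the 11:00 block at both. Among Group 2's change-from-Baseline efficacy scales, only the ESS changes its clock time. The C-SSRS, a safety scale, also moves from 8:00 to 10:30.

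**3. What cancels.** For a Group 2 subject, let c be the effect of rating at 10:30 rather than 8:00, τ the true effect of a dose on the past week's sleepiness, and a the acute effect of that morning's dose on the rating.

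- Active period: change from Baseline = τ + c + a
- Placebo period: change from Baseline = c
- Difference: τ + a

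The clock-time part c drops out, because placebo periods follow the same 10:30 schedule. I say largely, because c need not be constant over periods and the model also uses some between-subject information. The acute part a stays.

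**4. Is +1.5 h near peak?** It lies inside the stated tmax range of 1.3 to 3.0 h. As a rough check, assume a one-compartment model with first-order absorption at steady state, dosed every 24 h at the same time:

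C(t) ∝ exp(−ke·t)/(1 − exp(−24ke)) − exp(−ka·t)/(1 − exp(−24ka)),

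with ke = ln 2 / half-life and ka solved from tmax = ln(ka/ke)/(ka − ke).

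Example, tmax 3.0 h and half-life 5 h: ke = 0.139, ka = 0.66. Then C(1.5) ∝ 0.8425 − 0.3716 = 0.471, and the maximum, at 2.93 h, is 0.691 − 0.145 = 0.546. The ratio is 0.86.

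| tmax (h) | Half-life (h) | Level at +1.5 h, % of Cmax | Level at −1 h (23 h after the last dose), % of Cmax |
|---|---|---|---|
| 1.3 | 5 | 99.4 | 5.2 |
| 1.3 | 7.6 | 99.4 | 14.2 |
| 3.0 | 5 | 86.1 | 7.8 |
| 3.0 | 7.6 | 89.5 | 17.9 |

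The Group 2 rating therefore falls at about 86% to 99% of peak, and a Group 1 arrival-block rating at about 5% to 18%. The model form is assumed. Section 1.3.1 reports tmax after single and twice-daily dosing, whereas this trial doses once daily with breakfast soon after.

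**The case against.** **The ESS is not a momentary rating.** It asks about the past 7 days (Section 6.12.1) and about usual situations, including ones not recently met (Appendix 13). Nothing in the documents shows that alertness at completion moves the score. This stands. It limits the likely size of the acute part but does not show that it is zero.

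**The visible mismatch with Baseline mostly cancels.** This also stands. The 2.5 h shift affects the raw change from Baseline much more than the drug–placebo contrast.

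**The rule is soft.** It is worded as a recommendation with an approximate time, and Appendix 6 is a sample schedule. However, Section 7.3.2 carries both the rule and the conflicting order.

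**Group 1 is not uniformly at trough.** A reader might infer a clean contrast of peak in Group 2 against trough in Group 1. The documents do not support that. The Group 1 ESS may be done the day before the MWT, when the subject has dosed at home that morning, so it may be completed hours after a dose.

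**The ESS is not a confirmatory endpoint.** Safety is the primary objective, and SAP Section 16.1.2 tests no formal efficacy hypothesis and reports nominal p-values. This is fair, and it keeps the point small.

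**Conclusion.** The scheduling inconsistency is certain. Its consequence is possible but unquantified. What remains after cancellation is an acute drug effect on a 7-day recall score. If present, it would probably lower ESS on active drug and so favour it, and it would act in Group 2 more consistently than in Group 1. This rests on two assumptions: that the state at completion has some influence on the answers, and that drug level at +1.5 h is near peak, as the stated tmax suggests.

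A reader might go further and compute a bias as the Group 2 share times the acute effect per rating. The documents give neither quantity. Subjects choose their Group, and the ESS timing for those enrolled before Amendment 2 is not described here. Any product would be one assumption times another, so no figure is offered. Nor do the documents support calling the ESS result biased.

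A reader might also want the key model rerun without the post-dose ratings. That would remove every on-treatment Group 2 ESS taken to schedule and leave essentially a Group 1 analysis, which cannot separate timing from self-selection and loses power.

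This is a free improvement, not a flaw that puts the trial's conclusions at risk.

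**What to change.** 1. In Protocol Section 7.3.2 and Appendix 6, move the Group 2 ESS at Visits 3–6 to the pre-dose arrival slot (about −1 h, 8:00). This matches Group 2's own Baseline and the Group 1 arrival-block schedule, and it meets the protocol's timing rule.

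2. Apply the change to newly randomized subjects only. Doses ascend within Sequences A and B, so a switch partway through would put pre-dose and post-dose ratings in different dose periods of the same subject, and the clock-time effect would no longer cancel.

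3. For ratings already taken, add the by-Group ESS summary that Protocol Sections 9.12 and 9.15 leave optional to SAP Section 16.1.5 as a planned sensitivity analysis. State there that it can show a difference between Groups but cannot separate assessment timing from self-selection into Group.

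Cost: one self-completed questionnaire changes place within an existing visit, with no added time or procedure, plus one descriptive table. No sample-size figure changes.

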## Appendix 7 Caffeine Content of Beverages

Source	Serving Size	Typical caffeine (mg), range in parentheses
Coffee		
Brewed/drip	8 oz.	133 (71-280)
Espresso	1 oz.	70 (60-95)
Decaffeinated	8 oz.	5 (0-13)
Starbucks drip	12 oz.	260
Tea		
Brewed	8 oz.	53 (40-120)
Canned or bottled	12 oz.	20 (8-32)
Hot chocolate	6 oz.	7 (2-10)
Soft drinks		
Mountain Dew (& diet)	12 oz.	55
Diet Coke	12 oz.	47
[name] (& diet)	12 oz.	41
Sunkist	12 oz.	41
Pepsi (& diet)	12 oz.	36-38
Coke Classic	12 oz.	35
Barq's Root Beer	12 oz.	23
Energy drinks		
Red Bull	8.3 oz.	80
Rockstar	16 oz.	160
Medications*		
Exedrin Extra Strength	2 tablets	130
Anacin Adv. Headache	2 tablets	130
Midol Menstrual Complete	2 caplets	120
Weight loss supplements*		
Dexatrim Max	1 caplet	50
Hydroxycut Wt. Loss	2 caplets	200
Metabolife Ultra	2 caplets	150

\*Not an exhaustive list.

Source: Anderson BL, Juliano LM, Schulkin J. Caffeine's implications for women's health and survey of obstetrician-gynecologists' caffeine knowledge and assessment practices. *J Womens Health* 2009;18(9):1457-1466.

JZP-110

Clinical Trial Protocol: JZP166-201 Amendment 2

Jazz Pharmaceuticals

---

